6.2. Phase 1: Intervention Development. During the first 6 months of the project, we will formalize, manualize, and perform preliminary fidelity testing on three memory interventions targeting process-specific memory deficits after TBI in Veterans: (a) memory strategy training (to boost encoding), (b) errorless learning (to improve consolidation, and (c) retrieval practice (to rehabilitate deficits in retrieval).

6.2.1. Materials Common to Memory Interventions. Each of the three treatment conditions will utilize the same training materials, a set of verbal paired-associates (VPA) and a set of face-name pairs (FNP), both presented for training in associative learning. Each session will involve training utilizing two 12-item VPA lists and two sets of 12 FNP's, for an overall total of 144 unique VPAs and 144 FNPs. The VPA's are weak paired associates^{26,27} (have a forward association strength of <.01²⁸), and that do not contain words from clinical memory tests given in Phase 2. FNP's are constructed by pairing face-front black and white photographs from Stringer's Ecologically-Oriented Neurorehabilitation of Memory (EON-MEM) protocol²⁹. Training stimuli will be presented on a desktop computer using E-prime software.

6.2.2. Memory Strategy Training (MST). MST, in which persons with brain injury are taught specific strategies useful for encoding new information at the point of learning, is a widely used rehabilitative technique^{9,30,31} that is an *ACRM practice standard*¹⁵. While specific strategies vary across studies, most teach the participant to form meaningful cognitive associations between memoranda through the use of imagery or semantic encoding, building a form of memory encoding known as relational memory³². Relational encoding, a key process that enhances the strength and durability of episodic memory^{33,34}, can be reduced or impaired after TBI³⁵. Successful relational memory involves two distinct mnemonic mechanisms: the generation of an association between to-be-encoded items (a frontal/executive function)^{36,37} and the binding of that association into a cohesive memory trace (a function of the hippocampal memory system)^{33,38}. MST may be particularly useful in enhancing the first of these two processes.

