sentence (first list) or image (second list) that they created during encoding, and will then be asked to retrieve the target word again. Unsuccessful retrieval will be initially cued by the therapist. Prompted recall will also be recorded. This procedure will be repeated five times for each list, each followed by a retrieval phase. For each session, the dependent measure is the percentage of correct target words (out of 12) in spontaneous and cued recall for each list during the final exposure trial. For **FNP learning**, we will use a training approach adapted from Hampstead³⁹ and Stringer⁹. Training teaches patients to self-generate cues linking faces and names; patients will also be provided cues to standardize procedures and to encourage strategy development. For each FNP, participants will be directed to a salient facial feature (a visual cue like a long nose) and given a nickname that rhymes with the actual name (verbal cue) linking the feature to the name. Patients will be instructed to associate the visual and verbal cues by creating mental images that emphasize or exaggerate the relationship between cues. After initial learning, FNP's will be repeated five times. On each presentation, participants will be asked to recall the visual cue, then the verbal cue, and then finally the name. Dependent measure is the percent correct recall of visual cues, verbal cues, and names on the final trial of each list.

6.2.3. Errorless Learning (EL). EL refers to a group of techniques that promote recovery of memory abilities using procedures that explicitly prevent the patient from making errors during learning¹⁰. EL is based on the premise that errors during training become primed in long term memory via implicit memory mechanisms relatively spared in amnesia⁴⁰. Because of impairment in explicit memory consolidation that would normally provide corrective influence, these errors exert an unusually strong detrimental effect on relearning. While the standard interpretation of EL is that implicit memory is responsible for the treatment effect^{41,42}, it has been more recently shown that the EL advantage results from residual, though impaired, episodic memory consolidation due to temporal lobe damage^{43,44}. EL has been shown to be a promising tool in memory rehabilitation^{15,40,45}, at least for individuals without severe executive deficits⁴⁶.

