6.3. Phase 2: Patient Characterization and Classification

6.3.1. Participants. Veterans aged 25-65 who are post-deployment, having served in OIF, OEF, or OND, who meet criteria for moderate or severe TBI during deployment, are eligible to participate. *Patients will meet the 2007 VA/DoD criteria⁵⁴, supplemented by data from the VA TBI Identification Semi-Structured Interview⁵⁵.* All patients will have gone through Level I and II assessments with positive findings. Inclusion/Exclusion criteria: *Primary inclusion criteria:* M-STBI (blast and blunt), \geq 6 months post-injury, no receptive aphasia (impairing ability to comprehend task instructions), able to participate in return visits. *Primary exclusion criteria:* No MRI contraindications, not claustrophobic, no current or past history of disabling Axis I psychiatric disorders (except for PTSD and depression), no active substance abuse, not pregnant.

6.3.2. Procedure. Phase 2 consists of three components. **First**, after informed consent is obtained, participants undergo **standardized neuropsychological screening** to characterize their neurocognitive deficits, enabling comparisons with other Veterans whose memory rehabilitation outcomes have been reported in the literature. **Second**, we will use an established neuropsychometric algorithm to **classify patients into process-specific groups** that locates their primary memory deficit at the encoding, consolidation, or retrieval stage. **Third**, we will conduct **high-resolution structural and resting state functional MRI (RS-fMRI)** to determine whether our group classification is associated with different neuroimaging signatures. In this pilot proposal, we will not evaluate pre-post structural or functional brain changes resulting from our interventions, though this will be a key feature of a subsequent MERIT proposal based on our preliminary outcomes here.

6.3.2.1. Pre-Treatment Neuropsychological Screening. Table 1 lists key neuropsychological measures. Participants will be offered \$50 for participation in neuropsychological screening.

Domain	Measure
Effort	Test of Memory Malingering (TOMM)
Intelligence	North American Adult Reading Test (NAART) Wechsler Abbreviated Scale of Intelligence (WASI 2-subtest)
Memory	California Verbal Learning Test II (CVLT-II) Rey Complex Figure Test (Meyers version) – includes forced-choice effort measure Logical Memory, Visual Reproduction I, II (WMS-III LM, VR)

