6.5. Secondary Outcome Measures

We will collect preliminary data on secondary outcome measures (Table 5) derived from the Interagency Traumatic Brain Injury Outcomes Workgroup recommendations⁸⁶. Measures will be collected before treatment, immediately after the conclusion of each treatment (during the last treatment session), and 1 month after treatment has concluded. The \$50 paid to the participant to undergo post-treatment MRI scanning will also cover the collection of 1-month post-treatment secondary outcome measures, since they will be collected on the same day.

Table 5. Secondary Outcome Measures

Domain	Purpose	Measure
Global Outcome	Summarize overall TBI impact	MPAI-4
Memory Impairment	Characterize memory deficits	RAVLT, BVMT-R, Everyday memory simulations from EON-MEM ^a
Social Role Participation	Evaluate involvement and participation in life situations	CHART-SF
Self-reported and general Quality of Life	Perceived satisfaction and well-being	SWLS, QUOLIBRI
Patient Reported Outcomes	Evaluate outcome from patient evaluation perspective	PROMIS ^b and Neuro-QOL ^c Item Banks

^aAddress/Phone Number, News Article, Face-Name Learning simulations; ^bApplied Cognition-Abilities, Applied Cognition-General Concerns; ^cExecutive Function, General Concerns

7. Possible Discomforts and Risks:

7.1 **Risks Associated with MRI:** Magnetic resonance imaging (MRI) is a procedure that allows doctors to look inside the body by using a scanner that sends out a strong magnetic field and radio waves. This procedure is used routinely for medical care and is very safe for most people, but you will be monitored during the entire MRI scan in case any problems occur. The risks of MRI are:

- The MRI scanner contains a very strong magnet. Therefore, you may not be able to have the MRI if you have any type of metal implanted in your body, for example, any pacing device (such as a heart pacer), any metal in your eyes, or certain types of heart valves or brain aneurysm clips. Someone will ask you questions about this before you have the MRI.
- There is not much room inside the MRI scanner. You may be uncomfortable if you do not like to be in closed spaces ("claustrophobia"). During the procedure, you will be able to talk with the MRI staff through a speaker system, and, in the event of an emergency, you can tell them to stop the scan.

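### The rule keeping test items out of training does not reach the repeated outcome tests, one of which shares its source with the training faces

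*Protocol*

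**What the plan says.** Protocol section 6.2.1 describes one set of training materials for all three treatments: verbal paired associates (VPA) and face-name pairs (FNP). The VPA are chosen so that they "do not contain words from clinical memory tests given in Phase 2". That is the only item-exclusion rule in the available text. The FNP use photographs taken from the "Ecologically-Oriented Neurorehabilitation of Memory (EON-MEM) protocol". Nothing is said about keeping particular faces or names out.

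Table 5 (section 6.5) gives the memory outcomes as "RAVLT, BVMT-R, Everyday memory simulations from EON-MEM", and its footnote a names Face-Name Learning among the simulations. On timing: "Measures will be collected before treatment, immediately after the conclusion of each treatment (during the last treatment session), and 1 month after treatment has concluded".

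For the face-name part of memory strategy training (MST), section 6.2.2.1 says "we will use a training approach adapted from" two sources. One of these is the cited study of the EON-MEM rehabilitation approach (reference 9).

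**The concern.** The sponsor recognised that training items and test items must be kept apart, but the stated rule stops at Phase 2. The Phase 2 battery is headed as pre-treatment screening, and no repeat is scheduled. The tests given both before and after training are those in Table 5, and no rule covers them. For one of them, the training faces come from the same published package.

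At stake is how the Table 5 memory results are read. They are the study's evidence on whether training carries over to material that was not trained. If a test word, face or name was also a training item, the change from baseline mixes transfer with memory for that item. Section 5 says the results will be used to evaluate endpoints and to power a larger trial, so a contaminated transfer measure could be carried forward.

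**Working it through.** This is mainly a comparison of sections, with a few counts.

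**1. Tests the rule covers.** Table 1 (section 6.3.2.1) lists CVLT-II, the Rey figure, Logical Memory and Visual Reproduction under memory. RAVLT and EON-MEM are not listed. The rule applies to words in the VPA; it does not mention FNP.

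**2. Tests that are repeated.** Section 6.5 gives one assessment before treatment, one after each of two treatments and one at 1 month: 1 + 2 + 1 = 4 occasions. Three of the four follow at least one treatment, and two of those take place during a training session. Neither document mentions alternate forms, or says that the simulation uses untrained faces and names.

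**3. Exposure to training items.** Section 6.2.1 gives two 12-item lists of each kind per session, and section 6.4.2 gives six sessions per treatment.
- Bank size: 2 × 12 × 6 = 144 pairs of each kind, which reproduces the protocol's figure.
- Words in the VPA: 144 × 2 = 288.
- Two treatments without reuse would need 2 × 144 = 288 pairs of each kind. The stated total is 144, shared by all treatments, so on that reading each pair is met in both of a participant's treatments.
- MST and errorless learning (EL) each go through a list five times in a session.

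Any item that did overlap would therefore be well rehearsed before the later tests.

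**4. Size.** Let *f* be the share of test items that were also trained, and *a* the recall advantage of a trained item in percentage points. With no true transfer, apparent change = *f* × *a*. The documents give neither input. On assumed values:

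| Overlap *f* (assumed) | *a* = 10 | *a* = 20 | *a* = 40 |
|---|---|---|---|
| 0% | 0 | 0 | 0 |
| 25% | 2.5 | 5 | 10 |
| 50% | 5 | 10 | 20 |
| 100% | 10 | 20 | 40 |

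If a trained face reappears with a different name, *a* may be negative and the score may fall. The table shows how the bias scales; it does not estimate it.

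**5. Effect on matched versus mismatched.** All treatments use the same materials in counterbalanced order, so overlap alone gives this contrast no known direction.

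Similarity of method is a separate matter. Suppose MST has an additive advantage *d* on the Face-Name simulation that is unrelated to matching. From the orders in Table 4, with MST coded 1:
- Encoding (12, 13, 21, 31): MST is matched in 4 of 4, so the mean shift in matched minus mismatched is +*d*.
- Consolidation (21, 23, 12, 32): MST is mismatched in 2 of 4, so the mean shift is −2*d*/4 = −*d*/2.
- Retrieval (31, 32, 13, 23): MST is mismatched in 2 of 4, so the mean shift is −*d*/2.
- Pooled: (4*d* − 4*d* + 4 × 0)/12 = 0.

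With complete data the pooled contrast is unaffected. Individual and by-group contrasts are not protected, and SAP section 2.6 compares the treatments at the individual level.

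**The case against.** Several points on the other side are sound.

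- **No overlap is shown.** Only photographs are said to come from EON-MEM. The pairs are built by the study, the source of the names is not given, and the stimuli are to be set out in a treatment manual that is not among the documents. Stands: the gap is a missing safeguard and not a demonstrated fault.
- **The Phase 2 rule has a purpose.** A reader might infer that it guards tests that training cannot affect and so does nothing. That is not supported. Words already met in CVLT-II could prime or disturb VPA training scores, and those scores are Phase 3 dependent variables in the SAP. The rule should stay.
- **Only secondary measures are touched.** Section 6.5 calls these data preliminary, and SAP section 2.6 gives no specific analysis for RAVLT or EON-MEM. Stands, and it limits the weight of the point.
- **RAVLT may already be covered.** Table 1 lists key measures only, and Table 5 tests are also given before treatment, so the rule may be meant to include RAVLT. Possible, but the wording does not say so, and it would not close the face-name gap because the rule covers VPA words only.
- **Face-name testing is not special to MST.** EL and retrieval practice also train face-name pairs, and MST draws on two sources. Stands: the simulation is near transfer for all three treatments.

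**Conclusion.** The point holds as a gap in a stated safeguard. The rule leaves out the memory tests repeated across training, and the training faces share a source with one of them. Change from baseline on RAVLT and on the Face-Name simulation could therefore reflect trained items, in either direction, and not transfer.

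The size is unknown and may be zero; the figures in the working rest wholly on assumed overlap and recall advantage. BVMT-R and the self-report scales are not shown to be affected.

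A reader might go further and infer that observed gains are trained-item memory, or that overlap tilts the study towards or against matched treatment. The documents support neither. Overlap is not established, and common materials in counterbalanced order give it no known direction on that contrast. An MST advantage from similarity of method would cancel in the pooled contrast (4 matched, 4 mismatched, 4 without MST), assuming complete data and an additive effect. It could still affect individual or by-group comparisons. That is a separate issue, which an item rule does not cure.

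The change is worth making because it is nearly free and protects the transfer measures.

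**What to change.** 1. In section 6.2.1, keep the Phase 2 rule and extend it: training pairs contain no words, faces or names from any Table 5 memory test, including every RAVLT form used and the EON-MEM simulations.
2. Compare the item lists while the stimuli are built in Phase 1 and replace any that overlap. If training has already begun, report the overlap and score trained and untrained items separately.
3. Describe the Face-Name Learning simulation as near transfer for all three treatments. Note that the MST face-name method is partly adapted from related EON-MEM work, which can affect individual-level and by-group contrasts. Do not assume that the other EON-MEM simulations are neutral between treatments, since they come from the same package.

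Cost: a sentence or two of protocol text, a short item check and possibly a few replacement stimuli. No testing is added.

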6.2.2.1. Procedure. Six biweekly sessions of MST will be conducted. Two VPA lists and two FNP lists will be used in each session. During MST, VPAs (e.g., "candle-table") or FNPs will be presented in horizontal arrangement on a computer screen at a rate of 1 per 6 seconds (this may be modified based on participant processing speed). For **VPA learning**, participants will be asked to generate a memorable sentence (first list) or form a distinctive mental image (second list) that links the two VPA items together. The therapist will help the participant generate sentences and images that are distinctive or unusual, and therefore more memorable. Specific examples of distinctive sentence-based and imagery-based encoding will be given (e.g., "The wax from the candle poured onto the table", or an image of a candle scorching a table) and will be developed as the treatment is manualized. Immediately following list presentation, the cue word will be presented without the target (e.g., "candle-_____") and the participant will be asked to generate the target. Spontaneous production of targets will be recorded. For each item not spontaneously recalled, participants will be asked to retrieve the

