6.2.3.1. Procedure. Six biweekly sessions of EL will be conducted, each using two VPA lists and two FNP lists. During EL, the word pairs (e.g., "candle-table") or face-name pairs will be presented in horizontal arrangement on a computer screen at a rate of 1 per 6 seconds with no encoding instructions. After initial presentation, the cue will be presented without the target. For VPA learning, the cue word in each pair ("candle - _____") will be presented, and the participant will be asked to provide the second (target) word, ***but only if they are certain they can retrieve it accurately. Guessing is explicitly discouraged.*** If the participant cannot provide the word within 3 seconds, the word appears on the screen for 3 seconds and the participant is asked to read the pair aloud. During training, each list will be presented five times in this fashion. The dependent measure is the percent correct target words produced (out of 12) during the fifth exposure trial for each list. The procedure will be repeated for the second VPA list and then for the two FNP lists, yielding 4 accuracy measures (percent correct) for each session.

6.2.4. Retrieval Practice (RP). Some authors have argued that practicing retrieval during learning is an essential feature of successful learning^{10,47}. Effects of RP are most robust when retrieval is effortful, successful and spaced over time^{48,49}. If retrieval of a learned item is practiced shortly after it is learned, but before it is forgotten, subsequent recall is enhanced, a phenomenon known as the "testing effect"⁴⁷. RP has been used recently to improve performance of memory-impaired patients with multiple sclerosis⁵⁰ and M-STBI^{11,19}.

6.2.4.1. Procedure. Six biweekly sessions of RP will be conducted. We will follow procedures outlined in Sumkowski et al¹⁹, who demonstrated efficacy of RP in a small group of patients with M-STBI and chronic memory deficits. For each session, two sets of 12 VPA's and 12 FNP's will be used. Paired stimuli will be presented together for 6s on a computer screen, and the participant will be asked to read the VPA or say the name (FNP) aloud. Following this, 3 6s filler pairs (other VPA's or FNP's) will be presented. Then, a 5s cued

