## 2.6. Statistical Analysis Plan

The procedure for classifying participants into Encoding, Consolidation, and Retrieval groups is outlined in Section 2.3.2. It is recognized that, although patients will be classified according to their primary memory deficit, some may have relevant impairment in more than one domain. For this reason, each participant will be given a composite score for encoding, consolidation, and retrieval, and all three of these composite scores will be used in exploratory analyses of predictors of treatment response. Phase 2 neuropsychological scores (z-score transformed data using appropriate age- and education corrections) and neuroimaging data (NEW, FA, diffusivity measures, morphological volumes, TI from RS-fMRI for specific ROI pairs) will be analyzed using 1-way (Group: Encoding, Consolidation, Retrieval) ANOVAs followed by pairwise follow-ups with the Tukey HSD test. Dependent variables used to evaluate memory performance in Phase 3 are detailed in Section 2.2 above, and include session-wise percent correct data on VPA and FNP memory probes as well as post-treatment and 1-month follow-up probes. Data from Phase 3 will be analyzed by comparing effect sizes of matched and unmatched treatments at the individual subject level using methods described by Parker et al. These measures include (a) percentage of non-overlapping data points, (b) quantitative measures of improvement rate and difference level, and (c) Tau-U, a nonparametric measure of effect size that tests for differences in two treatments after trend adjustment. Additional measures will also be explored, including interrupted time-series/regression approaches and the last-day-of-treatment comparison approach. We will also evaluate the separate influence that severity of memory deficit has on treatment response (independent of patient grouping) by performing hierarchical linear regression in which severity is coded as average z-score on memory indices derived from phase 2, and patient grouping is dummy-coded.

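### The memory strategy training (MST) word-pair score mixes spontaneous and prompted recall over a fixed 12; spontaneous correct/12 should be named as the analysed score

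*Protocol*

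**What the plan says.** Protocol 6.2.2.1 describes the MST VPA test in two steps. The cue word is shown alone, and "Spontaneous production of targets will be recorded". Then comes a second attempt, restricted to the misses: "For each item not spontaneously recalled, participants will be asked to retrieve the" sentence or image they formed, and then to try the target again, with therapist cueing where needed. Of this step the protocol says "Prompted recall will also be recorded". The score to be taken from each session is given as "percentage of correct target words (out of 12) in spontaneous and cued recall for each list during the final exposure trial". The text does not say whether this is one cumulative percentage or two separate ones.

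The other two treatments have a single score with no second, prompted attempt. For errorless learning (EL), Protocol 6.2.3.1 says: "The dependent measure is the percent correct target words produced (out of 12) during the fifth exposure trial for each list". For retrieval practice (RP), Protocol 6.2.4.1 uses percent correct on a delayed test of each set.

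SAP 2.6 refers back to its Section 2.2 for the Phase 3 dependent variables; the matching content in the protocol is Section 6.2. It describes them as including "session-wise percent correct data on VPA and FNP memory probes", together with post-treatment and 1-month probes. These feed non-overlap, improvement-rate and level measures and Tau-U for each participant. No MST component is named.

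**The concern.** The number of items that can be scored as cued is 12 minus the spontaneous score, while the stated denominator stays at 12. A separate cued percentage therefore has a ceiling that moves down as the participant learns, and its trend need not follow memory. A combined percentage avoids that, but it gives MST a second, assisted chance at every missed item, which EL and RP do not give.

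The Phase 3 question is whether one treatment's session series lies above, or climbs faster than, another's in the same person. A score built differently in one of the two treatments enters that comparison directly. MST is the matched treatment for all four Encoding participants and the mismatched treatment for four others. A distorted MST score therefore pushes the matching comparison one way in the first four and the opposite way in the rest.

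**Working it through.** **Inputs from the documents.** 12 items per list, two VPA lists per session and six sessions (Protocol 6.2.1 and 6.2.2.1); only missed items are prompted; the denominator is 12. The one related figure that can be checked is the item total: 12 × 2 × 6 = 144, which agrees with "two 12-item VPA lists and two sets of 12 FNP's, for an overall total of 144 unique VPAs and 144 FNPs". The documents give no expected recall or cue-success rates, so the rates below are assumptions shown over a range.

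**Reach.** In Table 4, MST is treatment 1. It appears in Encoding 12, 13, 21, 31; Consolidation 21, 12; Retrieval 31, 13. That is 4 + 2 + 2 = 8 of 12 orders.

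**Formulas.** Let S be the items recalled spontaneously, s = S/12, and q the share of prompted items then recalled.
- Spontaneous: s
- Separate cued score: (1 − s)q, with ceiling 1 − s
- Combined score: s + (1 − s)q = 1 − (1 − s)(1 − q)
- Cued score over items actually cued: q

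**Ceiling of cued/12.** For S = 0, 3, 6, 9, 12 it is 100%, 75%, 50%, 25%, 0%. At q = 0.5 the score for S = 3, 6, 9, 12 is 37.5%, 25%, 12.5%, 0%.

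**Two example records.**
- Good learner, 10/12 spontaneous and 2 of 2 cued: cued/12 = 17%; combined 12/12 = 100%; spontaneous 83%; cued over items cued 100%.
- Poor learner, 4/12 spontaneous and 6 of 8 cued: cued/12 = 50%; combined 10/12 = 83%; spontaneous 33%; cued over items cued 75%.

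Cued/12 ranks the two the wrong way round, by 50 − 17 = 33 points. The combined score shrinks a spontaneous difference of 50 points (83 − 33) to 17 (100 − 83).

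**Trend over six sessions.** Spontaneous recall was drawn as Binomial(12, s) and cued recall as Binomial(12 − S, q), summed over two lists, with s and q linear over six sessions and 3,000 series per row. Expected scores come from the formulas; tau is the mean trend of cued/12 over sessions.

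| Spontaneous | Cue success | Cued/12 | Combined | Tau, cued/12 |
|---|---|---|---|---|
| 30→80% | 70% constant | 49→14% | 79→94% | −0.70 |
| 30→80% | 50→90% | 35→18% | 65→98% | −0.43 |
| 30→60% | 50→70% | 35→28% | 65→88% | −0.19 |
| 10→40% | 50→70% | 45→42% | 55→82% | −0.08 |
| 30→60% | 30→70% | 21→28% | 51→88% | +0.21 |
| 10→40% | 30→70% | 27→42% | 37→82% | +0.37 |
| 10→40% | 20→70% | 18→42% | 28→82% | +0.55 |

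Spontaneous recall rises in every row (tau +0.80 in the second). Cued/12 trends down in 91% of series in the second row and in 2% in the last.

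**Combined score.** It rises whenever s rises and q does not fall, because both (1 − s) and (1 − q) are then non-increasing. Its level is higher than the unaided one: at s = 30%, q = 50% it is 30 + 70 × 0.5 = 65%. Its gain equals the spontaneous gain plus the change in cued/12, so it can shrink or stretch. A 50-point gain shows as 98 − 65 = 33 or 94 − 79 = 15 points; in the last row a 30-point gain shows as 82 − 28 = 54.

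**The case against.** A reader might infer that the plan counts real improvement in MST as decline. The documents do not support that, for four reasons.

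- The measure is written in the singular and can be read as one cumulative score, for which 12 is the natural denominator and which does not fall as learning proceeds at steady or improving cue success.
- Even if the two components are scored separately, the SAP does not say that cued/12 is analysed alone, and spontaneous recall from the same trial would still show the gain.
- Only the ceiling of cued/12 must fall. MST trains people to form and retrieve the very sentence or image used at the prompted step, so cue success may well improve. The last three rows of the table then give a rising cued/12.
- The face-name half of the MST data is untouched, because visual cue, verbal cue and name are asked at each presentation. Post-treatment and 1-month probes are also used.

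One might add that Protocol 6.2.5 leaves methods of data collection to the treatment manuals, and that this is a 12-participant pilot.

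All of this stands against the strong claim. It does not make either reading a sound score. The cumulative reading still credits assisted answers to MST alone. A manual may settle what is recorded, but the SAP still has to say which score is compared.

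**Conclusion.** The point holds in limited form. As written, the MST VPA measure admits two scores, and both are worse for the Phase 3 comparison than spontaneous correct/12, which is already recorded. Cued/12 alone is not a valid measure of improvement: its ceiling moves with spontaneous recall, and the direction of its trend (tau about −0.70 to +0.55 in the cases tried) depends on cue-success rates that the documents do not give. The combined score keeps its direction if cue success does not drop, but it raises the MST level and distorts the size of the gain relative to EL and RP.

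The effect is confined to VPA data in 8 of 12 orders. The recall rates are assumptions; the ceiling, the 0% for a perfect learner and the presence of prompted answers in the combined score are not. Spontaneous recall is the closer counterpart to the EL and RP scores, not an identical one, since EL discourages guessing and RP tests after a delay.

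**What to change.** In Protocol 6.2.2.1 and SAP 2.6:

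- Name spontaneous correct/12 on the final trial of each list as the MST VPA session score for the non-overlap, improvement-rate, level and Tau-U comparisons.
- Report cued recall descriptively only, as cued correct/(12 − spontaneous correct), set to missing when no item was cued.
- State that neither stand-alone cued/12 nor the combined score enters those comparisons.

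The cost is a few sentences. No new data are needed, because spontaneous and prompted recall are already recorded separately. The one drawback is that the conditional cued score will be noisy or missing when few items are missed, which is tolerable for a descriptive result.
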